1 STUDY SYNOPSIS

Complete Protocol Title	Clinical Evaluation Of Vanguard Deep Dish Rotating Platform Knee
Protocol Number	BMETEU.CR.EU13B
Short Protocol Title	Vanguard Deep Dish
Sponsor	Biomet GS CC bv [name]
Manufacturer	Biomet Inc.
Study Device(s)	Vanguard DDRP Vanguard CR
Study Objectives/Endpoints	
Primary Endpoint American Knee Society Knee Score at 2-year post-operative.
 
Secondary Endpoint
 
- Patient success at 2 years postoperative- American Knee Society Score at each postoperative visit.- Radiographic evaluation at each postoperative visit.- Adverse events.- Survivorship at 10 year postoperative.
Indications/Target Population	Patients which are candidates for a total knee replacement because of gonarthrosis
Inclusion/Exclusion Criteria	
Inclusion criteria
 
1. Patients with a pre-operative knee score of < 70.2. Patients scheduled to undergo primary total knee replacement with any of the following indication:
a. Painful and disabled knee joint resulting from osteoarthritis.b. One or more compartments are involved.3. Need to obtain pain relief and improve function.4. Ability and willingness to follow instructions, including control of weight and activity level, and to return for follow-up evaluations.5. A good nutritional state of the patient.6. Full skeletal maturity of the patient, patients who are at least 18 years of age.7. Patients of either sex.8. Consent form read, understood, and signed by patient. 
Exclusion criteria
 
Absolute contraindications include the following diagnoses:
 
a. Patients with a pre-operative knee score of >70.b. Infection.

	
c. Osteomyelitis.d. Previous partial or total prosthetic knee replacement on the operative side.e. Skeletal immaturity of the patient, patients who are less than 18 years of age.f. Sepsis.g. Patients who had body mass index >40.
Study Design	International, multicenter, randomised, controlled trial
Clinical Phase	Post-market
Sample Size	A total of 340 study subjects implanted with the study device per cohort.
Length of Study	13 years (3 years of enrollment (all sites) and 10 years of follow-up)

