Materials and Methods	Case report forms were completed in hospital at Pre-op, Surgery, Immediate post-op, and the 6 week, 6 months, 1-year, 2-year, 3-year, 5-year, 7-year, and 10-year intervals visits.
Data Collection	Paper
Statistical Reporting	Data collected was summarized and reported to each participating investigator. Statistical analysis was conducted by Zimmer Biomet. Survivorship was evaluated using Kaplan-Meier.
Scores/Performance Assessments	Knee Society Score, Oxford Knee Score, WOMAC, Forgotten Joint Score and Lower Extremity Activity Scale.
Standards	
The PMCF is compliant with the below:
 
• ISO 14155: 2020 - Clinical investigation of medical devices for human subjects - Good clinical practice. (*) The study protocol may have been drafted according to another version of the ISO 14155. Adverse Event definitions and reporting are according to ISO 14155:2020.• The Declaration of Helsinki (DoH) - Ethical principles for medical research involving human subjects.
Study Funding	Funding for this clinical study is made available by Zimmer Biomet to support clinical data collection, IRB/EC review fees and other expenses associated with the conduct and execution of this study protocol as outlined in the fully executed Clinical Trial Agreement.

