2 STATISTICAL ANALYSIS PLAN

2.1 Sample Size

Patient populations for RCT group and NRCT group are determined based on non-inferiority test. Furthermore, non-inferiority is tested for both the primary endpoint and one of the secondary endpoints. Sample size calculation is conducted for each endpoint. The final patient number is the larger of the two sample sizes.

Endpoint – American Knee Society Score (KSS)

N=67 Correction for 15% Lost to Follow-up (approximately 7.5% each year): N=79

Endpoint: Patient success rate at 2 year postoperative:

N=127, Correction for 15% Lost to Follow-up (LTf) (approximately 7.5% each year): n=150

The final patient population is the larger of these two sample sizes. Therefore, 150 cases are needed each arm. To compensate for possible lost to follow up add 20 more patients each arm, hence, the total number of cases for RCT group is 340.

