2.2 Statistical Analysis

2.2.1 Descriptive statistics

Continuous outcome variables and their differences are analyzed with parametrical statistical techniques, such as t-tests, unless the normality assumption does not seem reasonable for the data, in which case non-parametric techniques are considered e.g. Wilcoxon/Mann-Whitney tests.

Categorical outcome variables are analyzed with chi-square tests and/or Fisher's exact tests (depending on the expected values in the categories). For the relevant parameters (subsidence, survival pain and function) also the 95 percent confidence intervals are calculated.

The effect of parameters such as age, sex and operators are evaluated using multiple variate analysis.

All data are analyzed by blinded researchers.

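### No missing-data method is given for the 2-year Knee Score: the named tests use only patients with a 2-year value, although 15% loss is planned

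*Combined protocol and SAP*

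**What the plan says.** The Study Synopsis sets the primary endpoint as "American Knee Society Knee Score at 2-year post-operative". Section 2.1 states that "non-inferiority is tested for both the primary endpoint and one of the secondary endpoints".

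For the knee score, section 2.1 gives "N=67 Correction for 15% Lost to Follow-up (approximately 7.5% each year): N=79". Patient success gets the same 15% correction (127 to 150), and 20 more patients per arm are then added against loss, giving 340 in the randomised group.

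On analysis, section 2.2.1 says "Continuous outcome variables and their differences are analyzed with parametrical statistical techniques, such as t-tests", with Wilcoxon/Mann-Whitney if normality looks unreasonable. It adds a multivariable look at factors such as age, sex and operator. It names no analysis set, no missing-data method, no repeated-measures model and no sensitivity analysis.

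The synopsis also shows what will be available before 2 years. Forms are completed pre-operatively, at surgery, and at "Immediate post-op, and the 6 week, 6 months, 1-year, 2-year, 3-year, 5-year, 7-year, and 10-year intervals visits". A secondary endpoint is "American Knee Society Score at each postoperative visit".

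**The concern.** A two-sample t-test or a Mann-Whitney test on the 2-year score cannot use a patient who has no 2-year score. With no other instruction, the primary comparison becomes an observed-case comparison of whoever returned at 2 years. Enlarging the sample protects power. It does nothing about bias if those who return differ from those who do not.

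Patients doing badly may be the ones who leave. If that happens to a different degree in the two arms, the observed arm difference no longer estimates the difference among all randomised patients. In a non-inferiority trial this can produce a false claim or hide a true one, depending on which arm loses its poor scorers. The earlier scores that could correct for part of this are already scheduled, but nothing in the plan brings them into the primary comparison.

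**Working it through.** **Plan's own figures.** Inflation for loss is n/(1 − 0.15). Knee score: 67/0.85 = 78.8, so 79. Patient success: 127/0.85 = 149.4, so 150. Both match section 2.1. The base figures 67 and 127 cannot be reproduced, because the margin, SD, success rates, alpha and power are not given.

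**Observed numbers at 2 years.** Section 2.1 gives 150 + 20 = 170 per arm. With 15% loss, 170 × 0.85 = 144.5 are observed and 25.5 are lost in each arm.

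**Is power the problem?** No. Assume that 67 per arm gave 80% power at one-sided 0.025. The implied margin is √(2/67) × (1.960 + 0.842) = 0.484 SD. With 144 per arm, power is Φ(0.484/√(2/144) − 1.960), about 98%.

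**Bias formula.** In one arm, the observed mean minus the full mean equals p × g, where p is the proportion lost and g is the mean 2-year score of observed minus lost patients. The bias in the arm difference (test minus control) is therefore p_T·g_T − p_C·g_C. With assumed gaps in SD units:

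- 15% loss in each arm, gap 0.5 in the test arm only: +0.075 SD (toward non-inferiority)
- 15% loss in each arm, gap 0.5 in both: 0
- 15% loss in each arm, gap 0.5 in the control arm only: −0.075 SD (against non-inferiority)
- 20% test versus 10% control, gap 0.5 in both: +0.05 SD
- 10% test versus 20% control, gap 0.5 in both: −0.05 SD

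**In score points.** Assume lost patients were d = 10 to 20 points lower at their last visit in both arms, and that this carries to 2 years with correlation r = 0.5 to 0.7. The size of the bias is then (difference in loss) × d × r:

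- 20% versus 10%: 0.10 × 10 × 0.5 = 0.5 to 0.10 × 20 × 0.7 = 1.4 points
- 18% versus 12%: 0.06 × 10 × 0.5 = 0.3 to 0.06 × 20 × 0.7 = 0.84 points

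The sign follows the arm with more loss. Using one r for every lost patient is a simplification: about half the planned loss falls in year 1, and those patients have no 1-year score.

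**Effect on the error rate.** Simulation with 6,000 trials per scenario. Assumptions: 170 per arm, 15% lost in each, true difference at the margin (0.484 SD), one-sided 0.025, correlation 0.6 between the 1-year and 2-year scores, every lost patient having a 1-year score, and selective loss driven by that score (logistic slope 1 per SD).

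| Low scorers lost from | Bias, observed cases | Type I error, observed cases | Type I error, 1-year score used |
|---|---|---|---|
| neither arm | 0.00 SD | 2.6% | 2.8% |
| test arm only | +0.08 SD | 9.8% | 2.4% |
| both arms alike | about 0 | 2.4% | 2.3% |
| control arm only | −0.08 SD | 0.4% | 2.4% |

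The simulation error near 2.5% is about √(0.025 × 0.975/6000) = 0.2 percentage points.

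**Precision.** Take 7.5% lost by year 1 and 15% by year 2. The relative variance of the observed-case mean is 1/0.85 = 1.176. Using the 1-year score it is (1 − r²)/0.85 + r²/0.925, which is 1.153 at r = 0.5 and 1.115 at r = 0.8. Effective numbers per arm are 170/1.153 = 147 and 170/1.115 = 152, against 144.5.

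**The case against.** Several points on the other side are sound.

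- A reader might infer that the plan restricts the 2-year comparison to patients seen at 2 years. It does not say so. The t-test is given as an example, in a section headed as descriptive, and imputation is neither stated nor excluded. What stands is that the only tests named for continuous outcomes need a 2-year value, and no text supplies another route.
- A reader might infer that the earlier scores are discarded. They are not: the score at each postoperative visit is a secondary endpoint. They are only absent from the primary comparison. If the word differences in section 2.2.1 means change from baseline, the pre-operative score would enter, but a patient without a 2-year score would still drop out.
- A reader might infer that 15% loss tilts the result toward non-inferiority. The documents do not support that. The same 15% is planned for each arm, nothing suggests differential loss, and the reverse pattern biases against the claim. Even loss strongly related to outcome leaves the arm difference about unbiased if it is the same in both arms.
- The sizes above rest on assumed gaps, correlations and loss rates. This is true, and unavoidable given what the documents report.
- A mixed model is not the only acceptable choice; multiple imputation is another. With the baseline score included, it also gives a baseline-adjusted estimate even with complete data, so it does not reproduce the t-test.
- Section 2.2.1 has the data analysed by blinded researchers. That limits a choice of method made to suit the result, but it does not protect against selective loss.

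These points narrow the concern. They do not supply the missing method.

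**Conclusion.** The concern holds as a gap in the primary analysis with a cheap remedy. The plan expects 15% loss, answers it with sample size alone, and names only tests that ignore patients without a 2-year score. The resulting comparison is safe if loss is unrelated to outcome or acts alike in both arms, and biased in either direction otherwise.

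The plausible size is modest in points: about 0.5 to 1.4 for 20% versus 10% loss under the stated gap and correlation. It can still matter for the error rate. In the assumed scenario with low scorers lost from the test arm only, the false non-inferiority rate rises from 2.5% nominal to 9.8%; with the arms reversed it falls to 0.4%. How serious this is against the trial's own margin cannot be judged, because the documents give no margin or SD. Neither power on the knee score nor precision is a main reason for the change.

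**What to change.** In section 2.2.1, make the primary analysis of the 2-year Knee Score a mixed model for repeated measures on the 6-week, 6-month, 1-year and 2-year scores. Include arm, visit, arm-by-visit and baseline-score-by-visit terms with an unstructured covariance, in all randomised patients with at least one postoperative score. Estimate the 2-year arm difference with its confidence interval and compare that interval with the non-inferiority margin.

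Keep the 2-year t-test, with its rank-test fallback, as a sensitivity analysis. Because that test shares the weakness described here, also add a sensitivity analysis for data missing not at random, such as a delta-adjusted or tipping-point analysis. Report loss by arm and visit alongside.

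The cost is SAP wording and slightly more programming, with no new visits, patients or data. The limitation that remains is that the primary model assumes loss is explained by the scores already observed, which is why the second sensitivity analysis is needed.

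### Section 2.2.1 names only unadjusted tests for a multicentre surgical trial, omits centre, and does not tie operator to the non-inferiority comparison, at a modest cost in precision

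*Combined protocol and SAP*

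**What the plan says.** The synopsis gives the design as "International, multicenter, randomised, controlled trial" and the primary endpoint as "American Knee Society Knee Score at 2-year post-operative". Section 2.1 adds that "non-inferiority is tested for both the primary endpoint and one of the secondary endpoints", the secondary one being patient success at 2 years.

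Section 2.2.1 contains the analysis methods:

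- Scores: "Continuous outcome variables and their differences are analyzed with parametrical statistical techniques, such as t-tests", with Wilcoxon/Mann-Whitney tests if normality is doubtful.
- Proportions: "Categorical outcome variables are analyzed with chi-square tests and/or Fisher's exact tests".
- Covariates: "The effect of parameters such as age, sex and operators are evaluated using multiple variate analysis".

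Neither centre nor country is named in sections 2.1 or 2.2. No stratified test and no stratification of the randomisation is described. No sentence says which analysis carries the non-inferiority conclusion.

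**The concern.** Knee replacement outcomes may differ by surgeon and hospital, and the plan itself treats operator as a possible influence. The named tests carry no term for either. Two consequences follow if they are used as they stand.

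- Variation between centres and operators stays in the residual, and chance imbalance of centres or operators between arms is not removed from the estimate. Non-inferiority is judged on where the confidence limit falls, so avoidable width counts directly against the conclusion.
- If the multivariable analysis does include arm, there will be an unadjusted and an adjusted answer for each endpoint and no rule for which one decides. That choice should not be open once results are known.

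**Working it through.** **1. The plan's own figures.** Inputs from section 2.1: "N=67 Correction for 15% Lost to Follow-up (approximately 7.5% each year): N=79" for the Knee Score; "N=127, Correction for 15% Lost to Follow-up (LTf) (approximately 7.5% each year): n=150" for patient success; then 20 more per arm and 340 in total.

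- 67 / 0.85 = 78.8, rounded up to 79.
- 127 / 0.85 = 149.4, rounded up to 150.
- 2 × (150 + 20) = 340.

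All three reproduce. The base figures 67 and 127 cannot be checked, because alpha, power, margin, SD and success rates are not given. Expected evaluable patients per arm after 15% loss: 170 × 0.85 = 144.5, so about 144.

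**2. Effect of adjustment on interval width.** The documents give no intraclass correlation (ICC, the share of Knee Score variance lying between centres) and no number of centres. Assumptions: ICC 0.03 to 0.15; 10 equal centres; 280 evaluable patients in all; the same arm effect in every centre.

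- Upper limit, arms balanced within centre: narrowing = 1 − √(1 − ICC).
- With only 10 centres, the pooled variance seen by the unadjusted test is about (1 − ICC) + ICC × 9/10 = 1 − ICC/10. Under centre-stratified randomisation the narrowing is therefore about 1 − √[(1 − ICC)/(1 − ICC/10)].
- Under simple randomisation, fitting centre also costs information on the arm contrast, by the factor 1 − 9/279 = 0.968. The narrowing is about 1 − √[(1 − ICC)/((1 − ICC/10) × 0.968)].

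| Assumed ICC | Upper limit | Centre-stratified | Simple |
|---|---|---|---|
| 0.03 | 1.5% | 1.4% | −0.3% |
| 0.05 | 2.5% | 2.3% | 0.7% |
| 0.10 | 5.1% | 4.7% | 3.1% |
| 0.15 | 7.8% | 7.1% | 5.6% |

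A simulation with the same settings agrees: about 1%, 2%, 5% and 7% (stratified) and 0%, 1%, 3% and 6% (simple). At ICC 0 with simple randomisation, adjustment would widen the interval by √(1/0.968) − 1, about 1.7%.

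**3. Validity of the unadjusted test.** A simulation (4,000 runs per setting, ICC 0.02 to 0.20, nominal one-sided level 0.025) gave type I error of 0.021 to 0.024 with simple randomisation and 0.016 to 0.027 with centre-stratified randomisation. The Monte Carlo standard error is √(0.025 × 0.975 / 4000) = 0.0025, so nothing points to inflation. The lowest value, 0.016 at ICC 0.20 with stratification, shows the unadjusted test becoming conservative.

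**4. Power.** Assumption: one-sided 0.025 and 80% power with N set on the total SD. Power after adjustment = Φ[(1.96 + 0.84)/√(1 − ICC) − 1.96]: 80.8% at ICC 0.02, 82.0% at 0.05, 84.0% at 0.10. These are upper values. Simulated power with simple randomisation and a shift of 0.33 SD, unadjusted against adjusted, was 0.79 and 0.79 at ICC 0.05, 0.79 and 0.80 at 0.10, and 0.80 and 0.85 at 0.20.

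**5. Reserve.** If the base sizes had been set on a within-centre SD, the unadjusted test would need N/(1 − ICC). The expected 144.5 per arm covers this up to ICC = 1 − 67/144.5 = 0.54 for the Knee Score and 1 − 127/144.5 = 0.12 for patient success. The second figure is approximate, since the formula is for a continuous outcome.

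**The case against.** The strongest reply is that the text is open-ended. Both the list of tests and the list of covariates are given as examples, so the multivariable analysis might contain arm and might contain centre. If each operator works in one centre, a fixed operator term would absorb centre differences as well. This stands. A reader might infer that operator is looked at only in a side analysis separate from the arm comparison, but the documents do not say so. What they show is that the link is not made, and that is enough to justify naming the model.

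A reader might also infer that imbalance of operators between arms biases the device comparison. It does not. Under randomisation the imbalance is a matter of chance, the unadjusted difference is unbiased, and its standard error already allows for the imbalance. Nor can it be inferred that the trial is too small: the Knee Score has more than twice the evaluable patients that section 2.1 asks for.

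Finally, the gain rests on an assumed ICC. That the forms are completed in hospital, as the synopsis states, is no evidence on how much raters or surgeons differ. This too stands, and it is why the result is given as a range that includes no gain.

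**Conclusion.** The point holds as a matter of precision and pre-specification. A multicentre surgical trial should state how centre enters the comparison that decides non-inferiority, and this plan does not. For the Knee Score the benefit of adjusting for centre is an interval narrower by roughly 0 to 6% (simple randomisation) or 1 to 7% (centre-stratified), given ICC 0.03 to 0.15 and 10 centres, none of which the documents supply. No comparable figure is offered for patient success, the endpoint that sets the sample size and has the thinner reserve: 127 needed against about 144 expected. The named tests remain valid for the randomised comparison. The change is worth making because it is standard, needs no extra patients, and removes the choice between an adjusted and an unadjusted answer.

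**What to change.** In section 2.2.1, for the randomised comparison:

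- **2-year Knee Score:** make the non-inferiority estimate the arm difference, with confidence interval, from a linear model with arm and centre. Use a random centre effect, or fixed centre terms with small centres pooled by a stated rule. Add operator within centre as a random effect only if numbers allow.
- **2-year patient success:** use a centre-stratified Mantel-Haenszel risk difference with confidence interval.
- **Supportive:** keep the unadjusted tests already named.
- **Status:** say that these two analyses carry the non-inferiority conclusions, and fix this before any between-arm results are seen. The synopsis reports the analysis in the past tense. If between-arm results are already known, the adjusted analysis should be labelled post hoc.

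The cost is a paragraph of SAP text, a little programming, a pooling rule for small centres and a few degrees of freedom. If centre effects are negligible there is a slight loss of precision, about 1.7% in interval width in the 10-centre example.

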2.2.2 Interim analysis (if applicable)

No interim analysis is performed, because it is expected that all patients are included in 6 months, so no patients will have obtained the primary outcome.

The 2, 5 and 10 years results may if possible be published in orthopedic journals and at scientific meetings.

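### Does the 6-month reason for having no interim analysis, set against 3 years of enrolment in the synopsis, call for a change to the plan?

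*Combined protocol and SAP*

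**What the plan says.** Section 2.2.2 of the SAP states without qualification that there will be no interim analysis, and gives as its reason that "it is expected that all patients are included in 6 months, so no patients will have obtained the primary outcome". The Length of Study row of the synopsis reads "13 years (3 years of enrollment (all sites) and 10 years of follow-up". The primary endpoint there is the "American Knee Society Knee Score at 2-year post-operative".

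Two statements concern release of results. Section 2.2.2 adds that "The 2, 5 and 10 years results may if possible be published in orthopedic journals and at scientific meetings". The Statistical Reporting row of the synopsis says "Data collected was summarized and reported to each participating investigator". Neither gives a date or a data cut, and the second does not say whether summaries are pooled or by arm. Section 2.2.1 adds that "All data are analyzed by blinded researchers".

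On numbers, section 2.1 says "Patient populations for RCT group and NRCT group are determined based on non-inferiority test". It puts the randomised group at 340.

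**The concern.** The two enrolment periods lie on opposite sides of the 2-year endpoint. If everyone is enrolled in 6 months, no one can have a 2-year score while enrolment is open. If enrolment takes 36 months, patients operated on in the first year reach the endpoint before it closes, so the inference in section 2.2.2 fails. Reading 6 months as a per-site figure does not rescue it: a site that enrols from month 0 to month 6 has its 2-year visits done by month 30, while other sites may still enrol until month 36.

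The worry that follows is about early release. On the 3-year plan, 2-year data exist from month 24 and accrue until month 60, and no sentence fixes when results by arm may first be produced. If results by arm reached investigators during the last 12 months of enrolment, they could influence who is enrolled or how knees are scored.

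**Working it through.** **Inputs.** Enrolment of 6 months (section 2.2.2) or 36 months (synopsis); primary endpoint at 24 months and follow-up of 10 years (synopsis); 127 evaluable patients per arm for patient success and 67 for the Knee Society Score, 15% loss over 2 years, 20 extra per arm, 340 in all (section 2.1). No accrual pattern is given.

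**The plan's own figures.**
- Study length: 3 + 10 = 13 years, as stated. With 6 months of enrolment it would be 0.5 + 10 = 10.5 years. The synopsis therefore rests on 3 years.
- Sample size: 67/0.85 = 78.8, rounded up to 79; 127/0.85 = 149.4, rounded up to 150; 2 × (150 + 20) = 340. All three match. The enrolment period enters none of them.

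**When the stated reason holds.** With even accrual over A months, the share of patients at 2 years when enrolment closes is max(0, (A − 24)/A).
- A = 6 or A = 24: 0.
- A = 30: 6/30 = 20%, or 68 of 340.
- A = 36: 12/36 = 33%, or 113 of 340, and 113.3 × 0.85 = 96 after the planned loss.

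If cumulative accrual over 36 months follows (t/36)^k, the share is (1/3)^k. A slow start (k = 2) gives 11%, or 38 patients; a fast start (k = 0.5) gives 58%, or 196. At 36 months the share is above zero whatever the shape, provided some patients are operated on in the first year.

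**Could that partial cohort pass for the 2-year result?** Evaluable patients per arm when enrolment closes:
- Even accrual: 96.3/2 = 48, below both 67 and 127.
- Fast start: 196.3 × 0.85/2 = 83, above 67 but below 127.
- Full cohort: 170 × 0.85 = 144.5, above 127.

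The plan takes the larger requirement as its basis. Under none of these accrual shapes would data available at the close of enrolment meet it.

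**What depends on the reason.** Type I error would be inflated by an unadjusted interim test, and none is planned. The decision not to look early is valid whether enrolment lasts 6 or 36 months.

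**The case for a change.** The strongest case for a change is that the gap between the two figures crosses the threshold at which the stated conclusion becomes false. Ruling out an interim analysis also does not by itself define the data cut for the 2-year analysis, which comes years before the study ends. Analyst blinding limits bias in the analysis but does not govern what is released or when. A sentence requiring one analysis by arm, after the last randomised patient's 2-year data are locked, would cost almost nothing.

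The first part stands: the figures conflict, and section 2.2.2 refers to all patients, so its wording cannot be confined to one site or one group. The rest does not carry the point further. Comparing arms at 2 years on part of the cohort is, in ordinary usage, an interim analysis, so section 2.2.2 already excludes it. Reading the publication sentence as permission to report a partial cohort means ignoring the commitment directly before it. The reporting line in the synopsis is in the past tense and mentions neither arms nor early summaries, so it shows no planned feedback by arm. A lock sentence would write down what a competent analyst would do anyway.

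The size of the overlap is also uncertain. Section 2.1 names a randomised and a non-randomised group, and the synopsis gives its 340 per cohort. The 3 years may therefore cover more than the randomised patients. If their enrolment took 24 months or less, the conclusion in section 2.2.2 would be true.

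**Conclusion.** The inconsistency is real, but no change to the plan follows. It is a clerical mismatch in the reason given for an acceptable decision. On 36 months of even accrual about 113 of 340 patients would have reached 2 years when enrolment closes (38 to 196 under the other shapes tried), and none if randomised enrolment takes 24 months or less. These counts rest on assumed accrual, before loss to follow-up. In every case the number of interim analyses stays at zero, the sample size stays at 340, and the type I error is unaffected. The conclusion rests on reading the unqualified commitment in section 2.2.2 as covering any comparison of arms on a partial 2-year cohort, which is its ordinary meaning. Aligning the two enrolment figures, or noting when the 2-year data are locked, would be editorial tidying with no gain for the result.
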